**MISTIE II Trial Design:** Stage 1 escalated the rt-PA dose (0.3 mg Q8hr, Tier 1 increased to 1.0 mg Q8hr, Tier 2) to test for dose response and safety. When compared to controls, both doses increased clot removal with no difference in bleeding rate (7% vs. 9%), leading to a decision to use the 1.0 mg dose. Tier 3 used the same precise image localization but a wider cannula and higher negative pressures (up to 300 mmHg) and is identified as the “ICES” Tier. We report on 123 subjects (117 MISTIE & medical; 6 ICES, medical only).

**MISTIE II Trial Safety:** The MIS+rt-PA procedure was evaluated for safety by dose, trial stage and comparison to medically treated subjects as defined by the MISTIE protocol utilizing AHA ICH guidelines. All emergent and ICU care was rendered according to guideline for each subject independent of randomization status. Of note, the influence of the withdrawal of care occurred equally among randomized subjects (surgical, 13%; medical, 10%).

**Mortality:** Data on intention-to-treat (54 surgical, 42 medical, n= 96) and all subjects (27 pilot, 96 randomized, n= 123) are provided. Including pilots, 81 subjects underwent MIS+rt-PA. There were no intra-operative deaths. Seven-day mortality was chosen as the immediate post-operative period; mortality was 2% in the MISTIE II cohort, comparing favorably to the 7-day mortality in FAST (12%-14%). The two deaths were related to the severity of the primary bleeding event, with cause of death preoperative respiratory failure (case1) and pre-existing coronary artery disease leading to postoperative myocardial infarction (case2). Thirty-day mortality was 10% and 15% for the medical and surgical groups respectively. No differences were noted for mortality at any time point, for the intention-to-treat, or the total group (Fig. 2). Withdrawal of care was equal in each group (36% vs. 53%) as well as the withdrawal of care temporal profile.

**Figure 2.** Kaplan Meier plot of mortality for randomized MISTIE II subjects. No differences were noted for mortality at any time point. Withdrawal of care was proportionally similar in both groups, and occurred at similar time frames in each group (Fischer's Exact Chi Square; non-significant).

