#### 6.2.5 On Study/Off-Intervention Evaluations

The follow-up phase of the protocol begins on day seven and continues through the 12-month follow-up visit. All subjects will be required to return for a follow-up clinic visit at months one, six, and 12, with a CT scan to be done at the one and 6 month visit. A telephone follow-up visit will occur at months three and nine. Daily monitoring of all adverse events will continue until day six. This includes monitoring of additional medications used, additional procedures and ICU care required. Serious adverse events will be monitored throughout the initial hospitalization. Serious adverse events, neurological adverse events, and total time at home (i.e., excluding hospital re-admissions and admission to rehabilitation facilities) will be recorded at all subsequent follow-up visits.

Subjects withdrawn early from the treatment protocol are asked to return to clinic for all scheduled follow-up assessments including the one, three (telephone contact), six, nine (telephone contact) and 12 month visits.

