#### **Efficacy Measures Summary.**

- **Primary measure:**

Dichotomized adjudicated mRS 0-3 vs. 4-6 at 180 days post-stroke

- **Secondary measures:**

1. Dichotomized adjudicated mRS at 365 days post-stroke 0-3 vs. 4-6 and 0-2 vs. 3-6
2. Ordinal adjudicated mRS (0 – 6) at 180 days post-stroke
3. Mortality and Safety Events at 30 days post-randomization, including procedure-related mortality, symptomatic bleeding rate, and infection rate
4. Mortality at 180 days post stroke
5. Functional Status: NIHSS, Barthel Index, GOS, extended GOS, MMSE at 180 days post-stroke
6. Type and intensity of ICU management: ICU days, hospital days, patient disposition at 180 and 365 days post-stroke

7. Quality of life: SIS, EQ-5D, PBSI, Personal Health Utility Assessment Interview, days to return to home; patient disposition at 180 and 365 days post-stroke including proportion of days in long-term care facilities
8. Cost: amount of billed and reimbursed

In addition to the primary and secondary measures, there are a number of related and intermediate surrogate outcomes of interest, including Glasgow Coma Score (GCS), Graeb Scale, clot lysis rate and final clot size reduction.

**Safety Measures.** Interim safety analyses will be prepared for the external Data Safety and Monitoring Board (DSMB) on a pre-arranged schedule (such as semi-annual or after enrollment of a fixed number of subjects) to evaluate efficacy and safety. Safety measures include: monitoring the incidence of symptomatic and asymptomatic intracranial bleeding events (i.e., hemorrhage extension, new hemorrhage, catheter-tract hemorrhage) through daily computerized tomography (CT) scans for the first four days after randomization and then repeated one day (approximately 24 hours) after ICH catheter removal, and monitoring the incidence of confirmed and suspected infection and in-hospital mortality.

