2.0. Objectives of the Study

2.1. Efficacy

The primary aim of this multicenter, international, randomized, open-label, phase 3 trial is to determine the efficacy of intra-clot catheter placement and aspiration of hematoma contents, followed by gentle clot irrigation with low dose recombinant tissue plasminogen activator (rt-PA), referred to as Minimally Invasive Surgery plus rt-PA (MIS+rt-PA). The primary hypothesis of this trial is that the MIS+rt-PA approach to intracerebral hemorrhage (ICH) management will result in more patients having overall better functional outcome at 365 days, as defined by the proportion of subjects with dichotomized, adjudicated modified Rankin Scale (mRS) score 0-3 vs. 4-6, when compared to the mRS scores for patients managed with standard aggressive medical treatment. Although the mRS includes a category for death, and hence the primary analysis incorporates mortality outcomes, in-hospital and 30-day mortality will also be examined as safety outcomes for the trial. Furthermore, 365-day mortality will be evaluated separately as a secondary efficacy outcome. An intent-to-treat (ITT) paradigm for the analyses will be incorporated. The MISTIE III trial will enroll a total of 500 eligible patients, 250 randomized each treatment arm (MIS+rt-PA or medical management). The power to detect (88%) is for an estimated effect size of 13% across all clot locations with this sample size (500).

Additional analyses of efficacy outcomes will evaluate the therapeutic benefit of MIS+rt-PA relevant to medical management in improving subjects' function and quality of life at 365 days post symptom onset as measured by extended Glasgow Outcome Scale (eGOS), days in various locations such as home

Minimally Invasive Surgery Plus rt-PA for ICH Evacuation Phase 3

during the 365-day period, patient disposition at 180 and 365 days including proportion of days in longterm care facilities, National Institutes of Health Stroke Scale (NIHSS), Barthel score, days in hospital, days in intensive care unit (ICU), Stroke Impact Scale (SIS), Preference-Based Stroke Index (PBSI), EuroQol-5 Dimension (EQ-5D), Mini-Mental State Examination (MMSE), Personal Health Utility Interview, and Center for Epidemiological Studies – Depression (CES-D).

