2.2. Efficacy Measures Summary: All Analyses Adjusted Similarly to the Primary Analysis

- **Primary Efficacy Analysis:** Dichotomized, adjudicated, cross-sectional mRS 0-3 vs. 4-6 at 365 days post-ictus, adjusting for baseline (pre-randomization) variables used in covariate adaptive randomization as well as the clinically established severity variables IVH size and ICH location (lobar or deep).
- Additional, Exploratory Analyses of mRS at 365 days:
 - a. Dichotomized, adjudicated, cross-sectional mRS 0-3 vs. 4-6 at 365 days post ictus, adjusting for baseline (pre-randomization) variables used in covariate adaptive randomization as well as additional baseline variables determined to be associated with the outcome.
 - b. Ordinal, adjudicated mRS (0-6) at 365 days.
 - c. mRS 0-3 vs. 4-6 at 365 days based on a full longitudinal analysis of the mRS data at 90, 180, and 270 days.
 - d. Severity subgroup analyses (including, but not limited to, IVH size, location of ICH, presentation co-morbidities such as diabetes, CVD, and white matter disease, etc.)
 - e. Cross-sectional of mRS 0-3 vs. 4-6 for demographic subgroups of patients, including for race and gender. (For d and e, see section 5.5.)
 - f. Analysis of cross-sectional mRS 0-3 vs. 4-6 at 365 days that models random effects for hospital sites.

• Secondary Analyses of other outcomes

- 1. Dichotomized eGOS UGR-US vs. LS-Death at 365 days.
 - Subordinate: Ordinal eGOS UGR, LGR, MD, LM, US vs. LS, VS, Death at 365 days.
- 2. All-cause mortality longitudinally from ictus to 365 days.
 - Subordinate: Predictors of mortality.
- 3. Relationship between clot removal as an AUC clot-assessment that estimates the timeweighted clot volume from ictus to end of treatment (EOT; i.e., 24 hours after last dose) as AUC clot exposure and functional outcome (proportion 0-3 mRS).
- 4. Patient disposition:
 - a. Home days over 365 days' time from ictus.
 - b. Patient location at 365 days post ictus (i.e., good vs. bad location. See Tertiary 2g for definition.)
- 5. 180-day efficacy:
 - a. Dichotomized, adjudicated, cross-sectional mRS 0-3 vs. 4-6.
 - Subordinate (1): Ordinal, adjudicated mRS (0-6).
 - b. Dichotomized, adjudicated eGOS UGR, LGR, MD, LM, US vs. LS, VS, Death.
 - Subordinate (2): Ordinal, eGOS UGR, LGR, MD, LM, US vs. LS, VS, Death.
 - Subordinate analyses 2-5 as defined under the Primary but for eGOS.
- 6. Type and intensity of ICU management:
 - a. ICU days

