13.4. Secondary Analysis 4: Patient Disposition

13.4.a. Secondary Efficacy Analysis 4a: Home Days Over 365 Days' Time from Ictus

Multivariable linear regression models will be built on this continuous outcome of time to home.

13.4.b. Secondary Efficacy Analysis 4b: Patient Location at 365 Days Post Ictus

Multivariable logistic regression models will be built on the dichotomized outcome of home plus rehabilitation locations versus other locations for patients 365 days post-ictus. Because variations in the more severe levels of mRS (4,5) and eGOS (US, LS, VS) do not fully account for disposition, it will be assessed by adjusting for all covariates. Where discrepant conclusions about severe disability might be drawn from mRS, eGOS, or final location, all three descriptors will be presented for the severe levels.

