15.3 Cost-Benefit Model

Cost-benefit analyses will be performed using data on median hospital stay, patient disposition categories (such as home, long-term ambulatory and nursing care, death), time to return home, and cost of procedures and hospital stay. These analyses will be performed with respect to both 180- and 365-day periods post-stroke. For cost-benefit analyses, the cost of ICU and the rest of the hospital stay, including the cost of MIS+rt-PA, will be considered. Cost data will be obtained from the literature. The overall amount for both treatments will be assessed, and the difference in dollars will be calculated.

Minimally Invasive Surgery Plus rt-PA for ICH Evacuation Phase 3

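### SAP 13.4.a names days at home as secondary outcome 4a but plans a regression of time to home, and gives no value for patients who die or never return home

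*SAP*

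**What the plan says.** The SAP lists outcome 4a in section 2.2 as "Home days over 365 days' time from ictus". The table of contents uses the same name, and the heading of section 13.4.a repeats it: "Secondary Efficacy Analysis 4a: Home Days Over 365 Days' Time from Ictus". One sentence follows that heading: "Multivariable linear regression models will be built on this continuous outcome of time to home".

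Elsewhere the two quantities are kept apart:

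- **Days at home.** SAP 2.1 speaks of "days in various locations such as home". Protocol 6.2.5 says that "total time at home (i.e., excluding hospital re-admissions and admission to rehabilitation facilities) will be recorded at all subsequent follow-up visits".
- **Time until return.** The quality-of-life item in the Protocol 9.1 list of efficacy measures has "days to return to home; patient disposition at 180 and 365 days post-stroke including proportion of days in long-term care facilities". SAP 15.3 takes "time to return home, and cost of procedures and hospital stay" as inputs to the cost model.

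On patients with no return home, SAP 2.2 puts death in the bad category for patient location (tertiary item 2g, to which 4b refers). No such rule is given for 4a. The censoring adjustment in SAP 9.0 and 11.1 is written for the primary mRS outcome, where death already has a score of 6. SAP 5.2 says that all efficacy outcomes are analysed by intent to treat. SAP 8.0 tests secondary outcomes at two-sided 0.05 without multiplicity correction.

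**The concern.** More days at home is good; a longer time to home is bad. An analyst cannot follow both the heading and the sentence under it, and the sentence is the only instruction on the model.

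The larger difference is in who has a value. Days at home can be counted for every patient, because someone who dies or stays in care simply has few or none. Time to home does not exist for someone who never gets there. Standard regression software drops records with a missing outcome. Unless a value is assigned, the fit would therefore rest on patients who survived and were discharged home, a group formed after randomization. If treatment affects who belongs to that group, the comparison is no longer a randomized one.

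At stake is the meaning of one named secondary efficacy result. If the variable and the handling of deaths stay open, they may be settled after treatment assignments are known, when the options can give different answers.

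**Working it through.** **1. No planned figure to reproduce.** The documents give no effect size, standard deviation or power for 4a.

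**2. The two variables side by side.**

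| | Days at home to day 365 | Time to home |
|---|---|---|
| Where used for 4a | SAP contents, 2.2, heading of 13.4.a | analysis sentence of 13.4.a |
| Better direction | higher | lower |
| Dies before going home, or never goes home | 0 days, if so defined | no value |
| Goes home, then is readmitted | readmission days not counted (Protocol 6.2.5) | unchanged |

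**3. Patients without a time to home.** Inputs: 250 per arm (SAP 2.1) and phase II mortality from Protocol 2.2, "Thirty-day mortality was 10% and 15% for the medical and surgical groups respectively".

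- Medical: 250 × 0.10 = 25.
- Surgical: 250 × 0.15 = 37.5, about 38.

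This assumes that the phase II rates apply and that none of these patients went home before dying. Later deaths and patients who never return would add to it. If 40% to 70% of medical patients return home within the year (an assumption; the documents give no figure), the number without a value in that arm is 250 × 0.30 = 75 to 250 × 0.60 = 150.

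**4. Can the two analyses disagree?** Assume a share *h* of medical patients goes home at mean day *t0*. The surgical arm has the same patients plus a further share *e* who go home at mean day *t1*. Return is permanent.

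- Time to home, returners only: difference = (*h·t0* + *e·t1*)/(*h* + *e*) − *t0*.
- Days at home, everyone: difference = *e*·(365 − *t1*).

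Take *h* = 0.50, *e* = 0.10, *t0* = 90 and *t1* = 200, all assumed:

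- Time to home: (45 + 20)/0.60 − 90 = 108.3 − 90 = +18.3 days, which reads as harm.
- Days at home: 0.10 × 165 = +16.5 days, a benefit.

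For *h* from 0.40 to 0.70 and *e* from 0.05 to 0.13, with (*t0*, *t1*) either (90, 200) or (60, 250), time to home differs by +7.3 to +46.6 days and days at home by +5.8 to +21.4.

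**5. Simulation of the same pattern.** Settings: 250 per arm, 3,000 replicates, *h* = 0.50, and unadjusted Welch tests at two-sided 0.05. Times to home were gamma (shape 2, mean 90) for the common returners and normal (mean 200, SD 50) for the extra ones.

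| Extra returners | Time to home worse and days at home better | Significant harm on time to home | Significant benefit on days at home |
|---|---|---|---|
| 5 points | 63% | 23% | 10% |
| 10 points | 90% | 60% | 25% |
| 13 points | 96% | 79% | 40% |

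**6. Cases without a reversal.**

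- *Extra returners as early as the rest* (*t1* = 90, *e* = 0.10): time to home differs by 0, while days at home gain 0.10 × 275 = 27.5. The benefit is missed, not reversed.
- *Same patients, faster return.* Protocol 2.2 reports 37 more days of care before return home in the phase II medical arm. If the returning share were the same in both arms, say 0.50, time to home would be 37 days shorter with surgery and days at home 0.50 × 37 = 18.5 higher. The measures agree.
- *Non-returners coded as 365.* The difference becomes *e*·(*t1* − 365) = 0.10 × (−165) = −16.5 days, which is the days-at-home result with its sign changed. The SAP states no such coding.

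**The case against.** The strongest reply is that this is a slip of wording. The sentence refers back to its own heading, the SAP calls 4a home days wherever it lists it, and the protocol collects total time at home. Time to home may just be loose wording for time at home. This is plausible. It is not certain, because the protocol does list days until return home as a measure and the SAP uses time to return home in its cost model. Under the benign reading, the text still needs reconciling and the value after death is still unstated.

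A reader might infer that the SAP restricts 4a to patients who reached home. It does not say so, and its intent-to-treat rule points the other way. Exclusion is only what a regression would do by default when no value is assigned.

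A reader might also infer that the planned analysis will reverse a true benefit. The documents do not support that. Every return-home rate above is assumed. Phase II found no mortality difference at any time point, so it shows no group saved by surgery and discharged late. Its one return-home figure favours surgery, and the two measures would then agree if the returning share is similar.

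The consequences are also contained. Mortality has its own secondary analysis in SAP 13.2, and 4b treats death as a bad location, so a survival effect distorting 4a would be visible beside them.

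**Conclusion.** The point holds as a contradiction and a gap in definition. SAP 13.4.a names one variable and models another, and no value is given for patients who die or never return home. Followed literally, the sentence gives an estimate on a selected subset, in conflict with SAP 5.2.

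A missed or reversed benefit is possible and depends on treatment changing who survives or returns home. The sizes shown illustrate the mechanism and do not predict the trial's result.

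The mortality figures are for scale only. They should not be read as a floor of 10% to 15% missing in each arm: the 10% is medical and the 15% surgical, they come from 42 and 54 randomized phase II patients, and carrying them over is an assumption.

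The effect is confined to one secondary outcome and its 180-day counterpart. The primary mRS analysis is untouched. A correction is worth making because it decides what 4a estimates.

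**What to change.** In SAP 13.4.a, replace time to home with the number of days at home from ictus to day 365, for every randomized patient. Count zero for days after death and for days not at home. Following Protocol 6.2.5, days in hospital readmission or a rehabilitation facility do not count as home. This should be stated, because 4b groups rehabilitation with home. Add a rule for patients lost to follow-up before day 365.

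The planned multivariable linear regression can stay: it then estimates a covariate-adjusted difference in mean days at home. A robust or bootstrap interval is preferable because many patients will have zero days, but that choice is optional.

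Use the same definition for home days at 180 days (SAP 2.2 tertiary item 2f and SAP 15.2.f). If time to home is also wanted, list it as a separate outcome with death as a competing event.

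The cost is a sentence or two in the SAP, settled before treatment assignments are seen. No new data are needed, since the protocol already records total time at home at the follow-up visits.

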13.5. Secondary Analysis 5: 180-Day Efficacy

13.5.a. Secondary Analysis 5a: Dichotomized, Adjudicated, Cross-Sectional mRS 0-3 vs. 4-6

Analysis methods described in section 11.1 for the Primary Efficacy Analysis will be repeated using day 180 data.

13.5.b. Dichotomized, adjudicated eGOS UGR-US vs. LS-Death

Analysis methods described in section 13.1 for the Secondary Efficacy Analysis 1 will be repeated using day 180 data.

13.5.1. Additional, Secondary Efficacy Analysis 5: Ordinal, Adjudicated mRS (0-6)

Analysis methods described in section 11.1.1. for the Subordinate Analysis (1) for the Primary Efficacy Analysis will be repeated using day 180 data.

13.5.2. Additional, Secondary Efficacy Analysis 5: Ordinal, eGOS UGR-US vs. LS-Death

Analysis methods described in section 13.1.1. for the Subordinate Analysis for Secondary Efficacy Analysis 1 will be repeated using day 180 data.

13.5.3. Additional, Secondary Efficacy Analysis 5: Subordinate Analyses 2-5 as Defined under the Primary Efficacy Analysis

Analysis methods described in sections 11.2–11.5 for the Primary Efficacy Analysis will be repeated using day 180 data.

Minimally Invasive Surgery Plus rt-PA for ICH Evacuation Phase 3

13.6. Secondary Efficacy Analysis 6: Type and Intensity of ICU Management

MIS+rt-PA treatment of ICH leads to decreased intensity of hospital care compared to medical management. This includes fewer hospital days, ICU days, decreased use or duration of ventilatory management, decreased intensity of ICP management, decreased BP support, decreased osmotherapy, shorter periods of CSF drainage, lower utilization of ventriculoperitoneal shunts, and fewer general critical care complications. Analyses: Linear, log-linear, and logistic data models will be similar to those presented above.

13.7. Secondary Efficacy Analysis 7: EQ-VAS and EQ-5D

Clot removal with MIS+rt-PA leads to improved health-related QOL and will be assessed by subject and surrogate QoL domains through the EQ-VAS and EQ-5D.

14.0. Safety Analyses

14.1. Mortality and Safety Events at 30 Days Post Randomization

The primary safety measures for this study are symptomatic intracranial bleeding, infection, and 30-day mortality. The safety thresholds for these measures have been set as: 30-day mortality >60%, a MIS+rt-PA–related symptomatic bleeding rate >25% (occurring during active treatment or during the 72 hours after treatment will be monitored), first-week operative death rate >10%, and a procedure-related infection rate >15% (over the initial 30 days). Bleeding will be further characterized as during the exposure to dosing of alteplase and the subsequent 72 hours. Comparisons to medical subjects in the same time frame will be made. Total SAEs at 30 and 180 days, as well as summary of AEs and SAEs by MedDRA code and grouped by organ system, will be compared by treatment groups.

Statistical Hypothesis: Early use of MIS+rt-PA for 3 days for the treatment of ICH is as safe as medically managed ICH, measured by rates of procedure-related mortality, rebleeding, and infection within 30 days post-randomization. The null hypothesis is: *Early use of MIS+rt-PA is worse than medical management for a specific safety measure.*

Analysis: The number of SAEs will be tabulated by SAE type post-stroke for the total population as well as by treatment group, with particular emphasis placed on group differences at 30 days post-randomization. Any treatment group differences in SAEs enumerated for interim analyses will remain blinded to investigators associated with this study. Unmasked results (e.g., group A versus B, where the labels "A" and "B" are randomly assigned to the surgical and medically managed groups) will be made available only during the closed sessions of DSMB meetings.

Methods of non-inferiority will be used to statistically determine if the proportions of a particular type of SAE, where there are adequate data for a particular type, are not substantially different among both treatment groups in order to test the hypothesis that MIS+rt-PA is as safe as standard medical management. Non-inferiority testing deems the rates of any SAE event in the MIS+rt-PA group to not be substantially greater than the SAE event rate in the standard medical management group as long as the group difference in this rate is statistically within some pre-specified tolerance. For this trial, the tolerance value will be defined as 10% for the primary adverse events of 30-day mortality, rebleeding, and infection, and 5% for first-week operative mortality. Thus, the rates of adverse events seen in the MIS group can be higher than those in the medically managed group, and yet still be considered not substantially different as long as the upper one-sided 95% CIs on rate differences are $\leq 10\%$ or $\leq 5\%$, depending on the safety measure.

Minimally Invasive Surgery Plus rt-PA for ICH Evacuation Phase 3

Since data from the MISTIE phase 2 trial neither supports nor negates any significant difference in SAE event rates by gender, race, or ethnicity, the non-inferiority analyses described above will be performed separately for subpopulations within each of these demographics where there are adequate data available.

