**Method of Dosing:** Subjects randomized to surgical management will receive 1.0 mg of rt-PA through the intraclot catheter every eight hours for up to nine doses. MISTIE II demonstrated that this dosage and route of administration is safe and balances clot dissolution against the complications of infection and symptomatic bleeding. Because the study is limited to nine or less doses, the total number of catheter openings will be similar

to or less than those in our previous IVH treatment safety study, which has an 8.3% rate of ventriculitis. MISTIE II further substantiated our choice of dosing every eight hours with a cerebral bacterial infection rate of 1%.

**Choice of Control:** The treatment group will be compared to the subjects receiving only conventional medical treatment. Subjects receiving MIS+rt-PA will be compared to an equal number of subjects randomized to receive conventional medical treatment. No vehicle controlled, placebo treated patients are planned in this study. This decision was made not to expose medically treated patients to the additional risk of surgical insertion of catheter. The medically treated patients do allow for the comparison of the intervention-induced complications that is the overall goal of this study, thus medically treated patients are the best overall control.

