**Specified Safety Measures:** Post-operative bleeding and infection occurred at low frequencies and below the literature-defined thresholds. Two brain infections were observed: culture-negative ventriculitis, surgical subject and culture-negative meningitis, medical subject. Both resolved without consequence. Recurrent bleeding rate was 5% overall: surgical, 2.65% (CI 0.07, 13.5), medical, 6.2% (CI 2.0, 13.8); pilot, 11%; randomized surgical, 3.7%; and randomized medical, 2.6%. It is difficult to attribute bleeding to the procedure or the drug; however, bleeding sites were frequently associated with the hematoma or catheter, preserving the need for caution of MIS+rt-PA as a trigger for increased likelihood of bleeding. MISTIE III will provide a better estimate of these rates. The overall rate of rebleeding (3.7%) compares well to the 10%-17% rate in other surgical and MIS trials.

[figure not shown]
**Edema:** Edema is an early indicator of tissue injury and is measured more easily in humans than cell death and ischemia. In MISTIE II, the protocol prospectively tested

[figure not shown]
the idea that clot reduction would lead to edema reduction as is observed in animals and preliminary data. Analysis of perihematomal regions of MISTIE II surgical subjects, utilizing a validated method, shows a reduction of 22 ml of edema when compared to medical subjects in the same time frame ( % reduction of 22±35 % surgical vs. increase of 47±46% medical). This finding is consistent with the reduction of toxic metabolic injury seen in animal models and inconsistent with a small number of prior “convenience samples” and clinical reports demonstrating an increase in edema after exposure to rt-PA. The Phase III will confirm the consistency of benefit across a broad population, the degree to which hematoma and edema reduction relates to improved functional performance, and the possible cellular basis of a beneficial effect.

**Functional Outcome Benefit:** ICH recovery requires more time than recovery from

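### The single 10-point safety tolerance can support an as-safe conclusion for rebleeding or infection on data that show a significant excess, and the plan does not say which result governs

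*SAP*

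**What the plan says.** Protocol 1.2 makes safety at 30 days a primary objective, judged on mortality, rebleeding and infection. SAP 14.1 gives the rule that decides it. Non-inferiority methods are used "to test the hypothesis that MIS+rt-PA is as safe as standard medical management". The margin is fixed in absolute terms: "the tolerance value will be defined as 10% for the primary adverse events of 30-day mortality, rebleeding, and infection", with 5 points for first-week operative mortality. A higher surgical rate is accepted "as long as the upper one-sided 95% CIs on rate differences are" at or below 10 or 5 points, according to the measure. Protocol 9.1.7.a (Analyses 1b) has the same numbers but calls the method equivalence. Neither document justifies the 10 points against expected event rates.

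On size, SAP 2.1 says: "The MISTIE III trial will enroll a total of 500 eligible patients, 250 randomized each treatment arm". SAP 8.0 says the study was not powered for safety.

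On phase II rates, Protocol 2.2 (Specified Safety Measures) gives rebleeding by randomized arm as "randomized surgical, 3.7%; and randomized medical, 2.6" per cent. It reports two brain infections, one surgical and one medical, both culture-negative. Protocol 2.2 (Mortality) gives 54 randomized surgical and 42 randomized medical patients, and 30-day mortality of 10% medical and 15% surgical.

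**The concern.** A margin of 10 points means different things at different event rates. For 30-day mortality, at 10% to 15% in phase II, it is of the same order as the event rate. For an event seen in 2% to 3% of controls it allows a several-fold increase.

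When the margin is that wide relative to the event rate, two statements can be true of the same data: the excess is within tolerance, and the excess is statistically significant. The plan attaches the hypothesis of safety to the first statement only. A trial could therefore report that the procedure is as safe as medical management for rebleeding while its own tables exclude equal risk. The conclusion at stake belongs to a primary objective.

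**Working it through.** **Inputs.** Tolerance 10 points and one-sided 95% limit (SAP 14.1). 250 per arm (SAP 2.1). Phase II medical rebleeding 2.6%, one medical brain infection, 42 medical patients (Protocol 2.2). The documents do not name the interval method. I use the Wald limit and check it against two others.

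**The plan's own figure.** No power is stated for the safety test, so I checked the sample size through the efficacy power in Protocol 9.1.9 (25% v 38%, 250 per arm, 88%). The mean rate is 0.315. The null SE is √(2 × 0.315 × 0.685/250) = 0.0415 and the alternative SE is √(0.25 × 0.75/250 + 0.38 × 0.62/250) = 0.0411. Power = Φ((0.13 − 1.96 × 0.0415)/0.0411) = 88.1%. The figure reproduces.

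**Tolerance against phase II medical rates.**
- Rebleeding: 10/2.6 = 3.8.
- Brain infection: 1/42 = 2.4%, and 10/2.4 = 4.2.

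**The rule applied.** Upper limit = d + 1.645 × SE, with SE = √(p₁q₁/250 + p₀q₀/250). For 6 medical and 22 surgical events, d = 8.8 − 2.4 = 6.4 points and SE = √(0.088 × 0.912/250 + 0.024 × 0.976/250) = 2.04 points. The upper limit is 6.4 + 1.645 × 2.04 = 9.75, a pass. The two-sided 95% interval is 6.4 ± 1.96 × 2.04, or +2.4 to +10.4.

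Largest surgical count that passes:

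| Medical | Surgical | Upper limit (points) | Two-sided 95% CI | Fisher p |
|---|---|---|---|---|
| 2 (0.8%) | 19 (7.6%) | 9.71 | +3.3 to +10.3 | 0.0002 |
| 3 (1.2%) | 20 (8.0%) | 9.84 | +3.2 to +10.4 | 0.0004 |
| 6 (2.4%) | 22 (8.8%) | 9.75 | +2.4 to +10.4 | 0.003 |
| 15 (6.0%) | 29 (11.6%) | 9.75 | +0.7 to +10.5 | 0.039 |
| 18 (7.2%) | 32 (12.8%) | 9.99 | +0.4 to +10.8 | 0.052 |
| 22 (8.8%) | 35 (14.0%) | 9.86 | −0.4 to +10.8 | 0.091 |

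With 6 medical events, every surgical count from 16 to 22 passes and is significantly worse by Fisher's test. Newcombe and Miettinen-Nurminen limits move the cut-offs by at most one event (6 v 21 under the latter, p = 0.005). By Fisher's test the overlap is down to one count at 6.0% and gone at 7.2%. By the Wald interval it is gone at 7.6% (19 of 250). Mortality at the phase II medical rate of 10% lies outside it.

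**How often (exact binomial enumeration).**

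| True rates, medical v surgical | Passes | Passes with Fisher p < 0.05 |
|---|---|---|
| 2.6% v 3.7% | >99% | 6% |
| 2.6% v 6.2% | 96% | 39% |
| 2.6% v 8.0% | 74% | 48% |

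**Arm labels in Protocol 2.2.** The same sentence also prints "surgical, 2.65% (CI 0.07, 13.5), medical, 6.2% (CI 2.0, 13.8"). Pilot 11% of 27 is 3 events and 3.7% of 54 is 2. Together that is 5/81 = 6.2%, exact 95% CI 2.0 to 13.8, which is the figure printed as medical; 81 is the number who underwent MIS+rt-PA. With 42 medical patients no whole count gives 6.2% (2/42 = 4.8%, 3/42 = 7.1%). The figure printed as surgical is close to 1/39 = 2.6% (0.06 to 13.5), near the randomized medical rate; the denominator of 39 is inferred and is not in the documents.

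**The case against.** **Significance inside a margin is inherent to non-inferiority.** SAP 14.1 says openly that the surgical rate may be higher and calls a pass not substantially different. That is fair, but the hypothesis under test is still worded as being as safe.

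**Harm would not be hidden.** SAP 14.3 plans Fisher's exact tests and mixed models on adverse events. SAP 14.1 compares bleeding with medical patients over the same time frame. The DSMB has review thresholds and stopping rules, and the protocol's adverse-event section requires expedited reporting of an imbalance between arms. This stands: a reader who infers that the excess would go unseen goes too far. What is missing is precedence. The thresholds (above 25% for bleeding, above 15% for infection) would not be reached at 8.8% or 8.0%.

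**The control rates are weak.** This stands too. Each rests on about one event, with an upper 95% limit near 13%. Protocol 2.2 also gives stage 1 bleeding of 7% and 9% without naming the groups; at either rate the ratio is 1.1 to 1.4 and the overlap is absent. Infection is not defined consistently: Protocol 9.1.8 refers to brain infection, while SAP 2.3 counts confirmed and suspected infection. The ratio of 4.2 assumes brain infection.

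**Stronger readings that the documents do not support.**
- A tolerance of 10 times the control rate. This uses the 1% in Protocol 2.1 ("dosing every eight hours with a cerebral bacterial infection rate of 1" per cent), a MISTIE II bacterial infection rate and not a control-arm rate.
- Near-certain certification of harm. The 96% at 2.6% v 6.2% is the chance of passing, not of passing with a significant excess (39%). The 6.2% also pools 27 non-randomized pilot patients and is set against randomized medical patients only.
- A tolerance derived from the mislabelled phase II rates. Neither document makes that link.

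**Conclusion.** The concern holds in a limited form. With 250 per arm and a medical-arm rate up to about 7%, SAP 14.1 can support an as-safe conclusion on data showing a statistically significant excess, and the plan does not say which result prevails. At 2.4% in controls the affected range is 6.4% to 8.8% in the surgical arm, up to a 3.7-fold increase. The finding does not depend on the interval method. It does depend on a low control rate, for which phase II gives only thin support, and for infection on the brain-infection definition. 30-day mortality at the phase II rate is not affected, and neither are the efficacy analysis, the sample size or data collection. This is a worthwhile, inexpensive tightening of a primary-objective conclusion. The arm labels in Protocol 2.2 are a separate, minor background matter.

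**What to change.** 1. Add to SAP 14.1 and Protocol 9.1.7.a (Analyses 1b): as safe is not concluded for any safety measure whose two-sided 95% confidence interval for the rate difference (MIS+rt-PA minus medical) lies wholly above zero; the result is then reported as an excess within, or beyond, the tolerance. Name the interval method and use it for both limits. This needs no assumed control rate. Cost: wording only, and a claim slightly harder to earn. At equal true rates about 2.5% of trials would lose it.

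2. Justify the tolerance separately for rebleeding and infection, and define infection. Five points, already used for first-week mortality, is one option. With equal true rates and 250 per arm, power is Φ(0.05/SE − 1.645): about 97% at 2.6% (SE 0.0142) and about 75% at 6.2% (SE 0.0216). It does not replace item 1, because 0 v 7 and 1 v 8 events still pass at 5 points with Fisher p = 0.015 and 0.037. Statisticians could reasonably choose another value.

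3. Separately, check the arm labels on the two rebleeding rates with confidence intervals in Protocol 2.2.
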